## 11 Data Handling and Record Keeping

### 11.1 Confidentiality

The clinical research staff in the Department of Ophthalmology at BMC has sole accessibility to view patient identifiers for eligibility review. After the patient is consented into the study, each patient will receive a unique study ID number to protect subject identity. Subject identifiers and study ID numbers will be linked in a secure, password-protected master database located in a departmental networked server, housed behind BMC's firewall. The master database will allow for subject re-identification, as necessary, for strict research-specific purposes. Only study personnel will have access to the master database.

Any paper records related to this study will be stored in locked cabinets or in a locked office. Any data that is analyzed by an outside source will not contain any identifiers. In the event that any information is stored on external storage, the data will be encrypted. Patient information will not be used in any other way than described in this protocol.

A description of this clinical trial will be available on <http://clinicaltrials.gov>, as required by U.S. Law. The website will not include information which can identify any of the subjects. At most, the website will include a summary of the results. The subject is able to search for the study at any time on the website by utilizing the ClinicalTrials.gov number shown on the first page of this protocol.

### 11.2 Source Documents

All source documents for this study will include the electronic medical record and the study-specific documents which includes the following:

- CRFs in Appendix section 15.2
- Patient Satisfaction Survey Appendix section 15.2.4
- AE, SAE, and UP tracking reports in Appendix section 15.4

Data generated by the methods described in the protocol may be recorded in the subjects' medical records and/or study progress notes. Data may be transcribed legibly on CRFs supplied for each subject or directly inputted into an electronic system or any combination thereof.

### 11.3 Case Report Forms

The study case report form (CRF) will be the primary data collection instrument for the study. All data requested on the CRF will be recorded. All missing data will be explained. If a space on the CRF is left blank because the procedure was not done or the question was not asked, "N/D" will be written. If the item is not applicable to the individual case, "N/A" will be written. All entries will be printed legibly in black ink. If any entry error has been made, to correct such an error, a single straight line will be drawn through the incorrect entry and the correct data will be entered above it. All such changes will be initialed

and dated. There will be no erasures or white-out on CRFs. For clarification of illegible or uncertain entries, the clarification will be printed above the item, then initialed and dated.

See the Appendix section 15.2 for the following CRFs: Eligibility Assessment Form, Documentation of Informed Consent, Home Study Diary, and the Satisfaction Survey.

#### 11.4 Study Records Retention

In accordance with BMC policy, the study records will be retained for at least seven years after completion of the study. Additionally, as required by the BMC/ BUMC IRB, documentation of informed consent of subjects will be retained for at least three years after the study is closed. All of the required records may be preserved in hard copy, electronic, or other media form and must be accessible for inspection and copying by authorized individuals.

## 12 Statistical Plan

### 12.1 Study Hypotheses

#### 12.1.1. Primary Objective: Intraocular Pressure

Formal hypothesis: Drop aids will be cost-effective in delivery of ophthalmic medications by improving baseline IOP measures to six week visit.

Testable hypothesis: Patient baseline IOP measures will be a statistically significant improvement in accordance to the usage of a drop aid device.

Null hypothesis: The patients, who are assigned to a drop aid device baseline IOP measures will not have a statistically significant change with the usage of a drop aid device when compared to patients not assigned to a drop aid device.

Alternate hypothesis: Patients not assigned to a drop aid device will result in larger significant change when compared to patients who are assigned to a drop aid device.

$$H_0: \mu_0 < \mu_d - \delta$$

$$H_A: \mu_0 \geq \mu_d - \delta$$

Where  $\mu_0$ , is the true mean IOP change from baseline to the six week visit without the drop aid device,  $\mu_d$  is the true mean IOP change from baseline to the six week visit with the drop aid device.

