## 4 Objectives

### 4.1 Study Objectives

The primary objective of this study is to compare efficiency of various drop aids for glaucoma medications objectively via changes in intraocular pressure. The different drop aids that are utilized are the Simply Touch Eye Drop Applicator, the Fabrication Autodrop Eye Drop Guide, and the Owen Mumford OP 6100 Autosqueeze. The central hypothesis is that the use of a drop aid device increases efficiency of glaucoma medication when comparing changes in intraocular pressure.

A secondary objective of this study is to evaluate how often a patient missed their eye when instilling drops with various drop aids in order to assess whether drop aids can decrease medication waste, increase medication compliance, and improve visual function. Additionally, the study will analyze how satisfied the patient is with their drop aid and the likelihood they would continue to use one outside of the study. These satisfaction means will be evaluated with a patient satisfaction survey approximately 3 weeks and 6 weeks after enrollment.

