### 12.1.3. Secondary Objective: Patient Satisfaction

Formal hypothesis: Drop aid devices will prove greater patient satisfaction than administrations without a drop aid device.

Testable hypothesis: Mean patient satisfaction to those assigned to a drop aid device compared to mean patient satisfaction scores to those not assigned to a drop aid device.

Null hypothesis: Patients assigned to a drop aid device will not show greater patient satisfaction than patients not assigned to a drop aid device.

Alternate hypothesis: Patients assigned to a drop aid device will show greater patient satisfaction than patients not assigned to a drop aid device.

$$H_0: \mu_s < \mu_{sd} - \delta$$

$$H_A: \mu_s \geq \mu_{sd} - \delta$$

Where  $\mu_s$ , is the mean patient satisfaction without the drop aid device,  $\mu_{sd}$  is the mean patient satisfaction with the drop aid device.

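### The worded primary alternative in 12.1.1 reverses the trial's central hypothesis, and the formula beside it cannot settle the direction because δ and the sign of change are undefined

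*Combined protocol and SAP*

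**What the plan says.** Section 4.1 gives the direction: "The central hypothesis is that the use of a drop aid device increases efficiency of glaucoma medication when comparing changes in intraocular pressure".

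Section 12.1.1 then states the primary hypothesis several ways:

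- Formal: "Drop aids will be cost-effective in delivery of ophthalmic medications by improving baseline IOP measures to six week visit".
- Testable: "Patient baseline IOP measures will be a statistically significant improvement in accordance to the usage of a drop aid device".
- Null, in words: no significant change with a device when compared with no device.
- Alternative, in words: "Patients not assigned to a drop aid device will result in larger significant change when compared to patients who are assigned" to a drop aid.
- Alternative, in symbols: "H_A: \mu_0 \geq \mu_d - \delta". The null is the strict opposite inequality.

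Here μ0 and μd are the true mean IOP changes from baseline to week six without and with a device. The section does not say whether a fall in IOP counts as positive or negative. δ has no value, sign or meaning there or elsewhere in section 12.

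The worded alternatives for the secondary objectives (12.1.2 to 12.1.4) all favour the device. For satisfaction (12.1.3) it is "Patients assigned to a drop aid device will show greater patient satisfaction than patients not assigned to a drop aid device", with symbols built on the same template as the primary.

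Section 12.3 names a paired t-test, before versus after within each patient, as the primary method. It refers to no null, alternative or margin.

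**The concern.** The alternative hypothesis fixes what a positive result means. Taken at its word, 12.1.1 would count a larger change in the control group as the positive finding. A reader would normally turn to the formula to settle a slip in the prose, but this formula can mean opposite things depending on two conventions that the plan leaves open.

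This is the only formal statement of the primary hypothesis. Section 12.3 fixes no sidedness, significance level or margin and leaves the list of methods open. Direction could therefore be assigned after the data are seen. The formal hypothesis also promises a conclusion on cost that the planned data cannot deliver.

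**Working it through.** **The plan's own figure.** Section 12.2 gives 10 patients in each of 4 groups: 10 × 4 = 40, which reproduces. It is set by budget. There is no power calculation, and the point does not depend on it.

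**Words.** Section 4.1, the formal hypothesis and the testable hypothesis point to the device. The worded alternative points to control. The worded null is one of no difference, while the symbolic null is a one-sided inequality, so words and symbols differ there too.

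**Symbols, H_A: μ0 ≥ μd − δ, with illustrative mmHg values.**

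- Change as reduction, device 3, control 1. With δ = 0, 1 < 3; with δ = 1, 1 < 2. Both satisfy H_0, so the working device sits in the null.
- Change as follow-up minus baseline, both groups −1, δ = 1. Then −1 ≥ −2, so a device with no effect sits in H_A. This is non-inferiority with margin δ.
- Change as follow-up minus baseline, device −3, control −1, δ = 0. Then −1 ≥ −3, so the working device is in H_A. With δ < 0, H_A requires the device to be better by at least |δ|. This is the one family of readings that favours the device.

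**Size of the ambiguity.** Assumptions, none from the documents: normal approximation, one-sided α = 0.025, SD of IOP change = 1, δ in SD units. Taking 10 controls against 30 pooled device patients, SE = √(1/10 + 1/30) = 0.365. The chance of concluding H_A is Φ[(μ0 − μd + δ)/SE − 1.96].

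| True device benefit (SD) | Reduction, δ = 0 | Reduction, δ = 1 | Signed, δ = 0 | Signed, δ = 1 |
|---|---|---|---|---|
| −0.5 (worse) | 27.7% | 98.4% | <0.1% | 27.7% |
| 0 | 2.5% | 78.2% | 2.5% | 78.2% |
| 0.5 | <0.1% | 27.7% | 27.7% | 98.4% |
| 1.0 | <0.1% | 2.5% | 78.2% | >99.9% |

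For example, signed change with δ = 0 and benefit 1 gives 1/0.365 − 1.96 = 0.78, and Φ(0.78) = 78.2%.

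The pattern does not depend on the split. With signed change, δ = 1 and no benefit, H_A is concluded 88.5% of the time with 20 versus 20, and 60.9% with 10 versus 10.

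**Section 12.1.3.** Taking higher scores as more satisfied, the symbolic null (μs < μsd − δ) contains the case where device patients are more satisfied by more than δ. The worded null says they are not more satisfied. For δ ≥ 0 the two contradict.

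**Whether 12.1.3 can be tested.** In the satisfaction survey (15.2.4), the only answer that fits a control patient on questions 1, 2, 3 and 5 is that they have no drop aid. Question 4 counts missed drops. Controls therefore yield no satisfaction score, and μs cannot be estimated.

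**Cost.** The diary (15.2.3) records bottle start and end dates, and 12.3 compares time to completion with controls. No prices or costs appear in Table 1, the diary or the survey, and 12.3 describes no cost analysis.

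**The case against.** The strongest reply is that the intended direction is plain from 4.1 and from the sentences around the alternative. Change from baseline to week six is naturally read as follow-up minus baseline. On that reading with δ = 0, the formula favours the device, and the odd sentence about larger change in controls may simply be μ0 ≥ μd put into words. This stands in part. A reader might infer that no reading of the formula tests benefit; that goes too far, since signed change with δ ≤ 0 does. But the plan states neither convention, carries a δ term without saying it is zero, and prints a worded alternative that, read ordinarily, says the opposite of its objective.

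A second reply is that 12.3 never uses H_0, H_A or δ, and 12.2 does not use them to set the sample size. This stands. A reader might infer that the trial will run a test in the wrong direction; the documents do not show that. The paired t-test looks at change within patients and does not test the between-group hypothesis in either direction. That limits the harm of the wording, but it also means that nothing in 12.3 repairs it.

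A third reply concerns cost. A reader might infer that nothing bearing on refills is recorded. That is not so: bottle dates are collected, and sections 3.1 and 3.2 link early bottle completion to refills and cost. What is missing is any cost data or cost analysis.

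**Conclusion.** The point holds. The worded primary alternative reverses the central, formal and testable hypotheses. The formula leaves the direction open: one family of conventions (signed change, δ ≤ 0) supports the device, and the others put a clearly working device in the null or reduce the claim to non-inferiority. The contradiction in words needs no assumption. The percentages rest on the assumed α, SD, δ and group split, and serve only to show how far the readings diverge.

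The error governs what may be concluded from the trial rather than any planned calculation, and it leaves the sample size of 40 unchanged. In 12.1.3, words and symbols contradict for δ ≥ 0; a reader might infer that correcting the symbols is enough, but the survey gives controls no score to compare. A cost-effectiveness conclusion is not supported by the planned data.

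**What to change.** - **12.1.1.** Define change as follow-up minus baseline IOP. State H_0: μd − μ0 = 0 against H_A: μd − μ0 ≠ 0, with a negative difference meaning benefit. Remove δ. Reword the alternative so that device patients have the greater IOP reduction. Say whether μd pools the three devices or is taken device by device. State the significance level; the two-sided form is a recommendation, as the plan gives no sidedness.
- **12.3.** Make the between-group comparison of IOP change the primary test, for example by linear regression on group and baseline IOP. Keep the paired t-test as a within-group description.
- **12.1.3.** Put the symbols in the device-favourable direction without δ. Then either add a satisfaction question that control patients can answer, or report satisfaction descriptively in the device groups only.
- **12.1.4.** Remove or define the same δ.
- **Formal hypothesis.** Replace cost-effective with effective.

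The cost is protocol wording, one changed analysis and, if wanted, one survey question. Visits, IOP data and N = 40 are unaffected.

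The corrected test would have limited power. With 10 versus 30 and an assumed two-sided α of 0.05, power is 27.7% at 0.5 SD, 59.1% at 0.8 SD and 78.2% at 1.0 SD. The difference detectable with 80% power is (1.96 + 0.84) × 0.365 = 1.02 SD (0.89 SD with 20 versus 20, 1.25 SD with 10 versus 10). The report should say so.

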### 5 Study Design

This interventional clinical trial is a prospective, single center, randomized controlled study. Patients being treated for their glaucoma at BMC's Yawkey Eye Clinic will be selected. Patients will be randomly placed, without manipulations by the principle investigator or any member of the research team, on one of the drop aid devices (including Fabrication Autodrop Eye Drop Guide, Simply Touch Eye Drop Applicator, Owen Mumford OP 6100 Autosqueeze), in addition to a no drop aid control, for a total of 4 groups.

Subjects have an equal chance of being randomized to one of the following study arms:

- Arm A: No intervention – Control
- Arm B: Active Comparator- Eye Drop Aids Including:
  - Simply Touch Eye Drop Applicator
  - Fabrication Autodrop Eye Drop Guide
  - Owen Mumford OP 6100 Autosqueeze

The primary endpoint is the comparison of baseline IOP measurement and follow-up IOP measurement. This comparison will determine the efficacy of using a drop aid. The secondary endpoints include the precision of the drop aid, patient satisfaction, and their likelihood to use a drop aid outside of the study. Data collection for assessment of study objectives will be obtained via standard of care clinic visits and completion of study diary and satisfaction survey by the patient with assistance of research team, if needed.

See the Appendix section 15.1 for a schematic of the study design and section 15.3 for drop aid labels and instructions.

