## 12.2 Sample Size Determination

The sample size was determined by the maximum number of subjects which could be randomized given the budgetary constraints of the grant funding. It was determined that a total of ten patients per group was financially feasible, thus a total of 40 patients will be enrolled in this study in approximately 1 year.

Enrolling the projected 40 subjects in 1 year is feasible, as the ophthalmology department sees approximately 275 glaucoma patients weekly. Due to the high volume of the glaucoma clinic, the study team should be able to easily recruit their target. Additionally, the study team is comprised of multiple

investigators and research assistants who have been delegated tasks on this protocol which can provide full-time recruitment coverage.

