### 12.3 Statistical Methods

A variety of statistical analysis will be used to analyze the results. A paired t-test will be the primary method of analysis. Any significant differences measured will be between the pre and post intervention, with the patient serving as their own control. However, the analysis will not be limited to a paired t-test and will also likely include ANOVA, chi-squared, p-value, linear regression, among others. Other outcomes such as length of time until completion of drops will also be measured and compared to no drop aid controls. Significant differences will be measured with similar statistical analysis as stated previously. Satisfaction of use will be measured with a survey and results will be averaged among those in the same cohort. Any significant differences will also be measured with similar statistical analysis stated previously.

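### The primary IOP analysis in 12.3 gives baseline IOP no role as a covariate; a prespecified ANCOVA would estimate the effect framed in 12.1.1 more precisely, at no data cost, in a trial fixed at 40 patients

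*Combined protocol and SAP*

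**What the plan says.** In section 12.1.1 the control parameter "is the true mean IOP change from baseline to the six week visit without the drop aid device"; the device parameter is defined in the same way, and the hypotheses compare the two. Section 5 is consistent with a change measure: "The primary endpoint is the comparison of baseline IOP measurement and follow-up IOP measurement". Section 5 also sets the structure, three devices "in addition to a no drop aid control, for a total of 4 groups".

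Section 12.3 is the only place where analyses are named. It says "A paired t-test will be the primary method of analysis", "with the patient serving as their own control", and that the analysis "will also likely include ANOVA, chi-squared, p-value, linear regression, among others". No outcome, model term or covariate is attached to any of these methods.

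Baseline IOP is available for everyone: section 9.2 has it measured on the day of enrollment, and the Schedule of Events in 15.1 puts the check at screening, before randomisation. Nowhere is it a covariate or a stratification factor.

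The sample cannot readily grow. Section 12.2 states: "The sample size was determined by the maximum number of subjects which could be randomized given the budgetary constraints of the grant funding".

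**The concern.** The contrast that 12.1.1 writes down is a between-group difference in change. If the team takes it literally and compares raw change between groups, the analysis subtracts the whole baseline value from each follow-up value. That is the best use of baseline only when the regression of follow-up on baseline has slope 1. With equal variances the slope is rho, which is below 1, so raw change over-corrects: a group that starts higher by chance tends to show a larger fall.

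Two things are at stake. The standard error is larger than it need be in a trial whose size was set by budget. And the estimate from the one trial actually run depends on how the baselines happened to fall, which with ten patients per group can be uneven.

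**Working it through.** **Inputs.** From the documents: ten per group and four groups (12.2, 5), effect framed as mean change (12.1.1), baseline IOP on every patient (9.2, 15.1). Not in the documents, so assumed: equal SD s at both visits, rho from 0.3 to 0.9, two-sided alpha 0.05, all 40 patients with a follow-up IOP.

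**The plan's own figure.** 4 × 10 = 40, which agrees with 12.2. There is no power calculation to reproduce. Pooling the devices gives 30 versus 10.

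**Precision.** For a between-group contrast:
- raw change: variance = 2(1 − rho) s² (1/n1 + 1/n2)
- ANCOVA, large sample: variance = (1 − rho²) s² (1/n1 + 1/n2)
- ratio = (1 − rho²) / [2(1 − rho)] = (1 + rho)/2

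Estimating the slope multiplies the ANCOVA variance by about 1 + 1/(N − 4): 1 + 1/36 = 1.028 for N = 40, and 1 + 1/16 = 1.0625 for a stand-alone 10 versus 10 model. Extra patients = 1/ratio − 1, using the 30 versus 10 ratio with slope cost. Detectable difference (80% power) and power for an illustrative 0.8 SD effect come from the noncentral t for 30 versus 10, shown as raw change → ANCOVA.

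| rho | (1+rho)/2 | 30 vs 10, with slope cost | Extra patients | Detectable difference, SD | Power at 0.8 SD | 10 vs 10, with slope cost |
|---|---|---|---|---|---|---|
| 0.3 | 0.65 | 0.67 | 50% | 1.24 → 1.02 | 44% → 60% | 0.69 |
| 0.5 | 0.75 | 0.77 | 30% | 1.05 → 0.92 | 57% → 68% | 0.80 |
| 0.7 | 0.85 | 0.87 | 14% | 0.81 → 0.76 | 79% → 84% | 0.90 |
| 0.8 | 0.90 | 0.93 | 8% | 0.66 → 0.64 | 92% → 94% | 0.96 |
| 0.9 | 0.95 | 0.98 | 2% | 0.47 → 0.46 | 99.8% → 99.8% | 1.01 |

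**Chance imbalance.** The difference in baseline means, in units of the patient SD, has SD sqrt(1/30 + 1/10) = 0.365 for 30 versus 10 and sqrt(1/10 + 1/10) = 0.447 for 10 versus 10. The probability that it exceeds 0.5 patient-SD in either direction is 2[1 − Φ(0.5/0.365)] = 0.171 and 2[1 − Φ(0.5/0.447)] = 0.264.

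A fraction (1 − rho) of the imbalance passes into the raw-change contrast. As an illustration, take a patient SD of 4 mmHg (assumed) and a typical 30 versus 10 imbalance of 0.365 patient-SD: 4 × 0.365 = 1.46 mmHg. The contrast shifts by 1.46 × 0.5 = 0.73 mmHg at rho 0.5, 1.46 × 0.2 = 0.29 at rho 0.8 and 1.46 × 0.1 = 0.15 at rho 0.9. The shift is proportional to the SD: at 3 or 5 mmHg the rho 0.5 figure becomes 0.55 or 0.91 mmHg.

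**Simulation check.** In 20,000 simulated trials of 10 versus 30 at each of rho 0.5, 0.7 and 0.9, with a true effect of 0.80 SD, both estimators averaged 0.80. The variance ratios were 0.76, 0.88 and 0.97, matching the table. The raw-change contrast correlated −0.51, −0.38 and −0.23 with the baseline imbalance; the ANCOVA estimate correlated at about 0.

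**The case against.** - **The definition in 12.1.1 is not wrong.** It defines population parameters, not an estimator, and under randomisation ANCOVA estimates the same between-group difference. A reader might infer that framing the effect as change is itself an error; the documents do not support that. This objection stands, and it places the fix in 12.3.
- **The plan does not name a between-group test of raw change for IOP.** Its named primary test is a within-patient paired t-test, which gives no between-arm contrast at all. That is the larger defect, and it must be replaced before adjustment can apply. This stands too. But replacing it with a t-test or ANOVA on change, the natural reading of 12.1.1, would leave the present problem in place.
- **Linear regression is listed.** It has no stated outcome, covariate or role. The documents show that no model is specified; a reader might infer a decision against adjustment, but they do not show one. The open list also leaves the choice between adjusted and unadjusted results until after the data are seen.
- **The change score is unbiased under randomisation.** Correct on average, and its standard error already includes the baseline variation. A reader might take the mmHg shifts above as bias; they hold only conditional on the imbalance observed. Nor does eligibility (7.1, 7.2) set an IOP threshold, so selection on high IOP is not driving regression to the mean.
- **The gain may be small.** Entry requires at least two months on the same medication, so a high rho is plausible, though unproven. This stands as a limit on size.

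**Conclusion.** The point holds as a weakness of the estimator in 12.3. The plan collects baseline IOP on every patient and specifies no adjustment for it, while the effect it wants is a between-group one. Relative to a raw-change comparison of 30 versus 10, ANCOVA cuts the variance by about 33%, 23%, 13%, 7% and 2% at rho 0.3, 0.5, 0.7, 0.8 and 0.9, and it removes the dependence on baseline imbalance. An imbalance above 0.5 patient-SD would arise in about 17% of trials (30 versus 10) or 26% (10 versus 10).

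Confidence is high that the covariate is missing and that adjustment is the better method. It is lower on the size of the gain, which rests on a rho that the documents do not give and on equal variances. Near rho 0.9 the gain is negligible, and in a stand-alone 10 versus 10 model it vanishes (ratio 1.01). The change should be made because it is nearly free, not because the unadjusted comparison would be invalid.

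**What to change.** In 12.3, replace the paired t-test as the primary IOP analysis with one ANCOVA across all 40 patients: follow-up IOP on randomised group (four levels) plus baseline IOP with a common slope. Make pooled devices versus control the primary contrast and each device versus control a further contrast, all with 95% confidence intervals. Estimating the slope from all 40 avoids the loss seen in separate 10 versus 10 models. Report raw change by group as description only. On this ground the definition of the effect in 12.1.1 can stay.

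The cost is one sentence and one degree of freedom, with no new data.
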